#### **4.9.5 Laboratory Data**

A detailed list of the laboratory parameters can be found in the CSP in section 4.5.6.

Laboratory parameters (hematology and chemistry) will be presented in shift tables of WHO toxicity grade at baseline versus worst grade post-baseline. Low/normal/high categories derived from investigator normal ranges will be listed. The reporting unit of laboratory values are SI units.

Selected laboratory parameters will be summarized in terms of mean, standard deviation, minimum, and maximum.

In calculating change from baseline at any scheduled Visit, only patients with non-missing values at both baseline and that Visit are included. All available data (i.e., scheduled and unscheduled assessments) are, however, used in identifying abnormalities in shift tables.

The laboratory data will be summarized in the following ways:

- 1) Summary statistics over time
- 2) Shift tables – this method requires the following:
  - a) type of categorization: WHO
  - b) time intervals of the shift defined – “shift from baseline” and “shift to worst value during treatment” intervals;
  - c) the worst assessment per laboratory parameter is selected per time interval, separately for hypo and hyper. Note, the worst assessment does not have to be unique as the table includes only the grade of the worst assessment.
- 3) Plots:
  - a) Mean Plots of Laboratory Parameters including 95% CI (Hematology and Biochemistry)  
CI interval should be calculated only for time points where there is data for at least 10 patients

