Hypercoagulation and risk of thrombosis	
 
• Investigators should be vigilant for patients who exhibit signs/symptoms consistent with thrombotic disease and should immediately begin work up and treatment as per local guidelines.
 
• If a patient has a thromboembolic event, further administration of emicizumab should be interrupted. The investigator must contact the Medical Monitor to assess if the clinical benefit clearly outweighs the risk to determine if the patient should resume taking emicizumab and discuss the patient's continued study participation.
 
• Please see Sections 0 and 0.9 for guidance on the management of breakthrough bleeds, including required laboratory monitoring.
 

TMA	
 
• Investigators should be vigilant for patients who exhibit signs/symptoms consistent with TMA and immediately begin work-up and treatment, as per local guidelines.
 
• If a patient has a TMA event, further administration of emicizumab should be interrupted. The decision to resume taking emicizumab after a TMA event must be discussed with and approved by the Medical Monitor.
 
• Please see Sections 0 and 0.9 for guidance on the management of breakthrough bleeds, including required laboratory monitoring.
 

ADA=anti-drug antibody; TMA=thrombotic microangiopathy

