## **6.4 SAFETY ANALYSES**

The primary objective of this study is to evaluate the overall safety and tolerability of prophylactic administration of emicizumab in patients with *congenital* hemophilia A who have *persistent* inhibitors against FVIII at enrollment. Of primary interest in this study are the incidence and severity of *all* adverse events, including thromboembolic *events*, *microangiopathic hemolytic anemia* or TMA, systemic hypersensitivity, anaphylaxis, and anaphylactoid events.

All adverse events will be assessed according to the WHO toxicity grading scale. The incidence, type, and grade of adverse events will be summarized according to the primary system-organ class (SOC) and, within each SOC, by Medical Dictionary for Regulatory Activities (MedDRA) preferred term. For each adverse event, data will be provided on the timing (start and stop date, time of onset in comparison with last dose of emicizumab received, and doses of emicizumab received), severity, relationship to *emicizumab*, outcome,

and effect on therapy. The data may be presented together with two-sided 95% Clopper-Pearson CIs if appropriate.

In addition, as part of the safety evaluation, additional assessments will be summarized descriptively as follows:

- Cumulative study medication doses, dose modifications (delays and interruptions), and duration of exposure
- Compliance with respect to emicizumab intake (planned vs. received)
- Changes from baseline in physical examination findings
- Vital signs over time:
  - Vital signs will be analyzed using descriptive statistics for continuous variables and presented graphically over time with associated 95% CIs.
- Laboratory parameters (hematology and chemistry):
  - These parameters will be presented in shift tables of WHO toxicity grade at baseline versus worst grade during the treatment period. Selected laboratory parameters will be summarized in terms of mean, standard deviation, minimum, and maximum. Laboratory parameters will also be presented graphically over time, *if appropriate*.

All safety variables will be analyzed for the safety population. For each variable, the number of available observations will be reported. The safety population includes all patients who have received at least one dose of *emicizumab*.

The primary safety analysis will occur at the end of the study.

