#### Before therapy:

All events/assessments that occur before the original study day 1 are considered to have occurred before therapy and have a negative study day. AEs occurring at the original study

day 1 are assumed to have occurred after therapy started. For handling of laboratory assessment, see definition of baseline.

Baseline:

Baseline assessment is the last valid assessment before or on original study day 1. As defined in the protocol, for all laboratory and immunogenicity assessments at the original study day 1, it is assumed that the assessment was done before the emicizumab intake. Baseline assessments that are measured only once at screening or week 1 and are not affected by treatment should be considered irrespective of the study day (e.g. gender, height, hemophilia history).

For Haem-A-QoL, Heamo-QoL-SF and EQ-5D-5L, the Week 1 questionnaire is considered to be the baseline irrespective of the collection date/time.

Up-titration Baseline:

For patients who are up-titrated, baseline for this period is defined as the last valid assessment done before or on Up-titration study day 1.

Treatment period:

Treatment period is defined as the time between original study day 1 and last emicizumab injection. For a patient who has not withdrawn from/completed treatment, the end of treatment period is actually defined as the date of the clinical cutoff.

Before up-titration:

The period before up-titration starts on the date of the original study day 1 and ends one day before Up-titration study day 1 or, in case of no Up-titration, either the date of study withdrawal or the cut-off date, whichever comes first.

After Up-Titration:

For patients who are up-titrated, the period after up-titration starts on the up-titration study day 1 and ends on the date of study withdrawal or the cut-off date, whichever comes first.

Follow-up:

Follow-up period starts on the day after the end of the treatment period. Follow-up period ends on the day of withdrawal, completion of follow-up, or at the end of the study as defined in the protocol. Only patients who have an assessment during this time period are considered as having entered follow-up.

Observation time:

Observation time is the time between date of enrollment and the day of death or the last actual assessment in the database (=last date known to be alive). At the time of a database cutoff for patients who have not withdrawn from the study, the cutoff date will be used instead of the last assessment date.

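### SAP 4.9.5 gives the laboratory shift table two conflicting windows, and the on-treatment one would leave out graded results obtained after the last dose

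*SAP*

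**What the plan says.** SAP 4.9.5 opens by describing "shift tables of WHO toxicity grade at baseline versus worst grade post-baseline". It adds: "All available data (i.e., scheduled and unscheduled assessments) are, however, used in identifying abnormalities in shift tables". Further down, item 2b sets the intervals for the shift and names the second one "shift to worst value during treatment". Item 2c then picks the worst assessment within each interval. Protocol 6.4 describes "shift tables of WHO toxicity grade at baseline versus worst grade during the treatment period".

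SAP 4.1 applies its period definitions to all outputs, naming laboratory data, unless something else is specified. There, "Treatment period is defined as the time between original study day 1 and last emicizumab injection". Patients still being treated are handled differently: "For a patient who has not withdrawn from/completed treatment, the end of treatment period is actually defined as the date of the clinical cutoff". After that, "Follow-up period starts on the day after the end of the treatment period".

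The Schedule of Activities collects hematology and chemistry at the Early Termination / Study Completion visit and at the Safety Follow-up Visit. Change in laboratory parameters is part of the primary endpoint (protocol section 2).

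**The concern.** The two phrases in 4.9.5 give different tables for the same patients, and nothing in the section says which governs. The on-treatment phrase has an awkward consequence in this trial. Protocol 5.1.2 has emicizumab interrupted after a thromboembolic or TMA event, and for TMA, "The decision to resume taking emicizumab after a TMA event must be discussed with and approved by the Medical Monitor". If dosing never resumes, the last injection comes before the work-up, and the platelet and creatinine results of that work-up lie outside the interval. If dosing resumes, the last injection moves later and identical values count. Whether an abnormal value enters the table would then depend on whether the patient stopped for good, which is itself related to how bad the event was.

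The AE summaries use a longer window. In patients who stop early, SAP 4.9.2 counts events until 24 weeks after the last dose or 2 years after the first, whichever comes first. The two parts of the primary safety endpoint would therefore cover different time spans in these patients.

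**Working it through.** The plan states no figure to reproduce here, so the check is mainly a comparison of definitions.

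**Step 1. What each reading keeps at the final analysis.**

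| Laboratory result | Opening sentence of 4.9.5 | Item 2b with SAP 4.1 |
|---|---|---|
| Event work-up, dosing later resumed | in | in |
| Event work-up after the last injection, dosing never resumed | in | out |
| Early Termination sample after the last dose | in | out |
| Safety Follow-up sample | in | out |
| 2-year sample on or before the day of the last injection | in | in |
| 2-year sample after the last injection | in | out |

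Patients still on treatment at an interim cutoff are unaffected, because their treatment period runs to the cutoff. At the final analysis everyone has completed or withdrawn (SAP 2.4), so the last-injection rule applies to all.

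**Step 2. Are the excluded results still exposed to drug?** Protocol 1.2.2.4 gives a half-life of 4–5 weeks, that is 28–35 days. The fraction remaining t days after the last dose is 0.5^(t / half-life):

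- t = 7: 0.5^(7/28) = 0.841 and 0.5^(7/35) = 0.871, or 84–87%.
- t = 30: 0.476 and 0.552, or 48–55%.
- t = 168 (24 weeks): 0.016 and 0.036, or 2–4%.

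Results in the first weeks after stopping are still under substantial exposure. A sample at 24 weeks is not.

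**Step 3. How many patients who stop for toxicity?** In the pooled program, 4 of 189 patients withdrew for adverse reactions (protocol 1.2.2.3). 4/189 = 2.1%, and 4/189 × 200 = 4.2, so about 4 here if the proportion carries over. The reactions listed are TMA, skin necrosis with superficial thrombophlebitis, and injection-site reaction. Some of these need not produce a graded hematology or chemistry shift, so the number whose worst grade would change lies between 0 and about 4, probably below 4. The carry-over is an assumption: median exposure in the pool was 38 weeks, against 2 years planned here.

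**Step 4. Completers.** Hematology and chemistry are scheduled at 18 months and 2 years, with none at the optional 21-month visit. With weekly doses from day 1, the last dose on or before day 730 is day 1 + 104 × 7 = 729. The 2-year visit at day 731 ± 30 spans days 701 to 761. The sample can therefore fall before, on or after the last injection. The protocol does not settle the order: the 2-year visit includes a PK sample, with pre-dose sampling and an in-clinic injection on PK days (4.5.6, 4.5.6.6), yet no drug is dispensed at that visit (Appendix 1). If the sample does follow the last dose, the final 6 of 24 months (25%) would contribute no scheduled sample to the table.

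**The case against.** The best defense is that the section can be read as keeping everything. Its opening sentence is unrestricted after baseline, all available data are said to be used, and item 2b does not use the defined term for the treatment period. This stands as far as it shows that the on-treatment window is not the SAP's settled rule, which a reader of item 2b alone might infer. It does not remove the conflict. The sentence on available data concerns scheduled versus unscheduled tests and sets no end date. Item 2b is the operational specification, SAP 4.1 is the default for laboratory data, and the protocol wording points the same way.

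Second, the information is largely reported elsewhere. Protocol 5.3.5.5 requires a laboratory result that changes study treatment to be reported as an AE. TMA and thromboembolic events are AESIs. The by-visit summaries and mean plots carry no on-treatment limit, and all values are listed. This stands. A reader might infer that toxicity behind discontinuation disappears from the report, and the documents do not support that. The AE tables are still not a full substitute, because the same protocol section says that not every laboratory abnormality is an AE.

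Third, an on-treatment shift table is a legitimate choice, and the protocol names it. That also stands. Different windows for laboratory and AE tables are not in themselves an error. The weakness is an inclusion rule that turns on permanent discontinuation, together with a section that states two rules.

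**Conclusion.** The inconsistency is real and should be resolved, because it leaves the end date of a primary-endpoint table open to choice at programming. The consequence is limited. Under item 2b, some patients' worst grade is understated: probably fewer than about 4 of 200 among those stopping for toxicity, assuming the pooled withdrawal proportion applies, plus an unknown number of completers whose 2-year sample follows the last injection.

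Three stronger readings are not supported:

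- Patients who stop permanently do not drop out of the table. They stay in it with their worst on-treatment grade.
- The figure of 4 of 200 is not a count of lost high grades. It is a rough ceiling under the stated assumption, since the pooled withdrawals include an injection-site reaction and skin necrosis.
- The 25% of exposure without a scheduled sample is conditional on a sampling order that the protocol leaves open.

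**What to change.** In SAP 4.9.5 item 2b, replace "shift to worst value during treatment" with: *shift to worst post-baseline value (scheduled and unscheduled) up to the later of the end of the AE reporting period (SAP 4.9.2) and the last study visit*. Give the opening sentence the same end date. The later of the two dates is needed because a completer's AE reporting period ends with the 2-year treatment period, while the 2-year visit may fall up to 30 days after its nominal date.

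State that this replaces the protocol 6.4 wording. State also how it combines with the general rule in SAP 4.9 that safety summary tables stop at up-titration. If an on-treatment table is wanted, show it second and label it as such.

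The cost is a change of SAP wording and one programming window. The table may show a few more high-grade shifts, some of them after the last dose.

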#### **Derived parameters**

- 1) Creatinine Clearance

The creatinine clearance will be derived based on the Cockcroft-Gault formula unadjusted and adjusted for body surface area (BSA). Both formulas are given below.

Unadjusted Cockcroft-Gault formula:

$$C_{CR} [ml/min] = \frac{(140 - Age [years]) \times Weight [kg] \times F}{0.8143 \times Creatinine [umol/l]}$$

where F=1 for male subjects and F=0.85 for female subjects

BSA-adjusted Cockcroft-Gault formula:

$$C_{CR-adj} [ml/min] = C_{CR}[ml/min] \times \frac{1.73 [m^2]}{BSA [m^2]}$$

## 2) Total Neutrophils

Total Neutrophils are derived as the sum of segmented and band Neutrophils. If one of the parameters is missing, it is assumed to be zero. Following this derivation, if there is more than one result per timepoint, the earliest record will be kept. If more than one result is at the same time, the smallest result is kept. In case the total neutrophils are reported together with the segmented and the bands, no calculation will be done and the total neutrophils are used.

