### WHO Toxicity Grading Scale for Determining the Severity of Laboratory Abnormalities and Adverse Events

Item	Grade 1 Toxicity	Grade 2 Toxicity	Grade 3 Toxicity	Grade 4 Toxicity
HEMATOLOGY				
Hemoglobin	9.5–10.5 g/dL	8.0–9.4 g/dL	6.5–7.9 g/dL	< 6.5 g/dL
Absolute neutrophil count	1000–1500/mm 	750–999/mm 	500–749/mm 	< 500/mm 
Platelets	75000–99999/mm 	50000–74999/mm 	20000–49999/mm 	< 20000/mm 
PT	1.01–1.25 × ULN	1.26–1.5 × ULN	1.51–3.0 × ULN	> 3 × ULN
aPTT	1.01–1.66 × ULN	1.67–2.33 × ULN	2.34–3 × ULN	> 3 × ULN
Fibrinogen	0.75–0.99 × LLN	0.50–0.74 × LLN	0.25–0.49 × LLN	< 0.25 × LLN
Fibrin split product	20–40 µg/mL	1–50 µg/mL	51–60 µg/mL	> 60 µg/mL
Methemoglobin	5%–9.9%	10.0%–14.9%	15.0%–19.9%	> 20%
LIVER ENZYMES				
AST (SGOT)	1.25–2.5 × ULN	2.6–5 × ULN	5.1–10 × ULN	> 10 × ULN
ALT (SGPT)	1.25–2.5 × ULN	2.6–5 × ULN	5.1–10 × ULN	> 10 × ULN
GGT	1.25–2.5 × ULN	2.6–5 × ULN	5.1–10 × ULN	> 10 × ULN
Alkaline phosphatase	1.25–2.5 × ULN	2.6–5 × ULN	5.1–10 × ULN	> 10 × ULN
Amylase	1.1–1.5 × ULN	1.6–2.0 × ULN	2.1–5.0 × ULN	> 5.0 × ULN
CHEMISTRIES				
Hyponatremia	130–135 mEq/L	123–129 mEq/L	116–122 mEq/L	< 116 or mental status changes or seizures
Hypernatremia	146–150 mEq/L	151–157 mEq/L	158–165 mEq/L	> 165 mEq/L or mental status changes or seizures

Item	Grade 1 Toxicity	Grade 2 Toxicity	Grade 3 Toxicity	Grade 4 Toxicity
Hypokalemia	3.0–3.4 mEq/L	2.5–2.9 mEq/L	2.0–2.4 mEq/L or intensive replacement Rx required or hospitalization required	< 2.0 mEq/L or paresis or ileus or life-threatening arrhythmia
Hyperkalemia	5.6–6.0 mEq/L	6.1–6.5 mEq/L	6.6–7.0 mEq/L	> 7.0 mEq/L or life-threatening arrhythmia
Hypoglycemia	55–64 mg/dL	40–54 mg/dL	30–39 mg/dL	< 30 mg/dL or mental status changes or coma
Hyperglycemia (note if fasting)	116–160 mg/dL	161–250 mg/dL	251–500 mg/dL	> 500 mg/dL or ketoacidosis or seizures
Hypocalcemia (corrected for albumin)	8.4–7.8 mg/dL	7.7–7.0 mg/dL	6.9–6.1 mg/dL	< 6.1 mg/dL or life-threatening arrhythmia or tetany
Hypercalcemia (correct for albumin)	10.6–11.5 mg/dL	11.6–12.5 mg/dL	12.6–13.5 mg/dL	> 13.5 mg/dL life-threatening arrhythmia
Hypomagnesemia	1.4–1.2 mEq/L	1.1–0.9 mEq/L	0.8–0.6 mEq/L	0.6 mEq/L or life-threatening arrhythmia
Hypophosphatemia	2.0–2.4 mg/dL	1.5–1.9 mg/dL or replacement Rx required	1.0–1.4 mg/dL intensive Rx or hospitalization required	< 1.0 mg/dL or life-threatening arrhythmia

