
Efficacy periods:

The start of the efficacy period for each individual starts on the date of first emicizumab treatment. The end of the efficacy period is defined as the date of the clinical cutoff or the date of withdrawal from/completion of the treatment whichever is earlier.

For patients who withdraw from the study before reaching the Week 1 visit, the duration of efficacy period is set to 1 day, and it starts and ends on the day of enrollment.

For patients whose dose is up-titrated, the efficacy period ends one day prior to the first day on the up-titrated dose (Efficacy period 1).

For patients whose dose is up-titrated, the bleeds occurring during the administration of the up-titrated dose are analyzed separately. The efficacy period on the up-titrated dose starts with the first day on this dose and ends on the day of the clinical cutoff or the date of withdrawal from/completion of treatment (Efficacy period 2).

For statistical evaluations (e.g. descriptive summaries) of post-baseline data summarized by visit, only measurements at scheduled visits are considered. If a measurement is repeated at a scheduled visit (or time point), then only the latest retest result will be used in calculation of the statistical summary. All data – including unscheduled measurements – will be included in the listings.

If a time interval was calculated in minutes, hours or days and needs to be converted into months or years the following conversion factors will be used:

1 year = 365.25 days

1 month = 30.4375 days

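### When a record has a band count but no segmented count, the SAP's zero rule makes the bands the total neutrophil count and can give a patient with a normal count WHO grade 3 or 4

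*SAP*

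**What the plan says.** The Total Neutrophils paragraph under the derived parameters of SAP 4.9.5 contains four rules.

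- Derivation: "Total Neutrophils are derived as the sum of segmented and band Neutrophils".
- Missing component: "If one of the parameters is missing, it is assumed to be zero". The sentence treats the two components alike.
- Duplicates: "if there is more than one result per timepoint, the earliest record will be kept", and "If more than one result is at the same time, the smallest result is kept".
- Reported total: "In case the total neutrophils are reported together with the segmented and the bands, no calculation will be done"; the reported value is then used.

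SAP 4.9.5 sends hematology to "shift tables of WHO toxicity grade at baseline versus worst grade post-baseline" and says that both scheduled and unscheduled results count when abnormalities are identified for those tables. The row labelled "Absolute neutrophil count" in Protocol Appendix 5 gives the cut-offs: grade 1 is 1000–1500/mm3, grade 2 is 750–999, grade 3 is 500–749 and grade 4 is below 500.

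SAP 4.11 gives imputation rules for bleeds and their treatments only. Nothing there changes the neutrophil rule. For repeats at a scheduled visit, SAP 4.1 has a general rule for by-visit summaries: "then only the latest retest result will be used in calculation of the statistical summary".

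**The concern.** Zero is a sensible stand-in for a band count, which is usually a small part of the total. It is not sensible for the segmented count, which is usually nearly all of it. When that component is missing, the sum is not a slightly low estimate of the total. It is a different quantity, and it is then graded against cut-offs meant for the total.

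A worst-grade table has no averaging to dilute the error: one affected record decides the patient's post-baseline cell. If the record is the baseline one, the patient starts from a falsely high grade and a true later fall may not appear as a shift. Changes in laboratory parameters are listed under the primary objective (Protocol Section 2), and hematology abnormalities go to the iDMC (Protocol 9.4.1).

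The rule is also out of line with the SAP's own practice. Missing adverse event severity is left unknown (4.9.2), and aPTT samples with no detected clot are excluded (4.10).

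**Working it through.** The plan states no figure of its own on this point, so there is nothing to reproduce. The check applies the rule as written and grades the result.

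**Step 1: the rule with segmented missing.** Derived total = segmented + bands = 0 + bands. With true total T and band share f, the derived total is f × T. T and f are assumptions, since the documents give neither. Every T below is above 1500/mm3 and so truly ungraded. Cells show the derived total per mm3, with the WHO grade in brackets.

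| T | f = 0% | 1% | 3% | 5% | 10% | 15% |
|---|---|---|---|---|---|---|
| 2000 | 0 (4) | 20 (4) | 60 (4) | 100 (4) | 200 (4) | 300 (4) |
| 3500 | 0 (4) | 35 (4) | 105 (4) | 175 (4) | 350 (4) | 525 (3) |
| 5000 | 0 (4) | 50 (4) | 150 (4) | 250 (4) | 500 (3) | 750 (2) |
| 7500 | 0 (4) | 75 (4) | 225 (4) | 375 (4) | 750 (2) | 1125 (1) |

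Of 24 combinations, 19 give grade 4 and 2 give grade 3, so 21 are falsely severe. Two give grade 2 and one gives grade 1. Every combination with a band share of 5% or less gives grade 4.

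**Step 2: the rule with bands missing.** Derived total = (1 − f) × T. A truly ungraded count falls to grade 1 only if (1 − f) × T ≤ 1500, that is T ≤ 1500/(1 − f). This is 1500/0.99 = 1515/mm3 at 1% bands and 1500/0.85 = 1764/mm3 at 15%. Over true totals from 300 to 7999/mm3 and shares of 1% to 15%, the error never exceeds one grade, and an ungraded count never becomes grade 3 or 4. The two components therefore need different handling.

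**Step 3: does the reported-total sentence prevent it?** Read literally, it applies when the total arrives with both components. A record with a total and bands but no segmented count is outside its wording. If a reported total and a derived sum, or a complete and a partial record, are held for the same time, the smallest-value rule picks the artefact.

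**Step 4: from records to patients.** The schedule of activities has 9 scheduled post-baseline hematology visits: Weeks 2, 3 and 5; Months 3, 6, 9, 12 and 18; and 2 years. Let q be the share of records with bands, no segmented count and no total used. q is an assumption, and visits are taken as independent. The chance that a patient has at least one such record is 1 − (1 − q)^9.

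| q | Chance per patient | Expected among 200 |
|---|---|---|
| 0.1% | 0.9% | 1.8 |
| 0.5% | 4.4% | 8.8 |
| 1% | 8.6% | 17.3 |

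These rows show sensitivity to q. They do not predict what will happen in this trial.

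**Step 5: repeats.** The neutrophil paragraph keeps the earliest record per timepoint; SAP 4.1 keeps the latest retest in by-visit summaries; the shift tables are meant to use everything. If the earliest-record rule is applied before the shift table is built, a later and lower genuine value at the same timepoint is lost.

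**The case against.** The strongest reply is that the rule may never run. Protocol 4.5.6.1 lists neutrophils as a single item of the differential and names neither segmented nor band counts, and scheduled hematology goes to a central laboratory. If that laboratory reports a total, the derivation is only a fallback. The reported-total sentence was probably meant to give the total precedence in every case. This stands as an argument about frequency. It does not cure the wording, and the SAP plainly foresees separately reported components with one missing. Local results needed for safety assessment can also enter through unscheduled-visit forms (Protocol 4.5.6), and unscheduled results count in the shift tables.

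A reader might infer that the trial's primary safety results will contain false severe neutropenia. The documents do not support that. Nothing shows that a record with bands alone exists. The adverse event tables would not change, because under Protocol 5.3.5.5 a laboratory result becomes an adverse event through symptoms, a treatment change, an intervention or the investigator's judgment, and a value created at analysis meets none of these. All analyses are declared descriptive, so no error rate is involved.

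A reader might also infer that the earliest-record rule contradicts SAP 4.1. It can equally be read as a specific rule overriding a general one. What is missing is a statement of which outputs it governs.

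**Conclusion.** The rule is wrong as written for one case: bands present, segmented count absent, no reported total used. In that case a band count below 500/mm3 is graded 4 and one of 500–749/mm3 is graded 3, regardless of the true count. Grade 3 or 4 is not automatic, since band counts of 750/mm3 or more give grade 2 or lower. One affected record is enough to set a patient's worst post-baseline grade or to inflate the baseline grade.

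Confidence is high about the wording and its arithmetic, and low about any practical effect, because the frequency is unknown and probably low. The reach is limited to descriptive laboratory outputs, chiefly the neutrophil row of the shift table. This is a minor correction, worth making because it costs almost nothing.

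**What to change.** Replace the missing-component and reported-total sentences in SAP 4.9.5 with an ordered rule:

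1. If a total neutrophil count is reported, use it, whether or not either component is present.
2. Otherwise, if the segmented count is present and bands are missing, set bands to zero and add.
3. Otherwise, if the segmented count is missing, leave the total missing.

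This removes every false grade 3 or 4 that arises from a missing segmented count. What remains is the missing-band error of at most one grade shown in Step 2.

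Separately, add a sentence stating that the one-record-per-timepoint rule applies to by-visit summaries only, cross-reference it to the latest-retest rule in SAP 4.1 and say which of the two governs total neutrophils. State also that the shift tables use all results, as SAP 4.9.5 already intends.

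The cost is two or three SAP sentences and a matching line in the derivation specification. No data collection changes.

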## **4. STATISTICAL METHODS**

No formal statistical hypothesis tests will be performed and all analyses are considered descriptive.

Categorical data will be summarized using frequencies and percentages (including a category for missing, if appropriate). Continuous data will be summarized using descriptive statistics (N, mean, standard deviation, median, lower quartile, upper quartile, minimum and maximum). Other analysis methods will be specified (below) where applicable.

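### Total neutrophils: the SAP keeps the earliest of repeated results at a timepoint, which contradicts its own latest-retest rule and, read literally, its all-data rule for shift tables (minor)

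*SAP*

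**What the plan says.** Three passages of the current SAP bear on a neutrophil count measured more than once at one timepoint.

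- **SAP 4.9.5, Derived parameters, Total Neutrophils.** The total is the sum of segmented and band cells. After that derivation, "if there is more than one result per timepoint, the earliest record will be kept". For ties in time, "If more than one result is at the same time, the smallest result is kept". A laboratory-reported total takes precedence: "In case the total neutrophils are reported together with the segmented and the bands, no calculation will be done and the total neutrophils are used".
- **SAP 4.1, Reporting Periods.** For post-baseline data summarised by visit, where several measurements exist for one planned visit or timepoint, the choice is the reverse: "then only the latest retest result will be used in calculation of the statistical summary".
- **SAP 4.9.5, main text.** "All available data (i.e., scheduled and unscheduled assessments) are, however, used in identifying abnormalities in shift tables". For the shift tables, "the worst assessment per laboratory parameter is selected per time interval, separately for hypo and hyper".

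The neutrophil paragraph gives no reason for preferring the earliest record. It does not call itself an exception to 4.1, and it does not say which outputs it applies to. The other two derived parameters, creatinine clearance and corrected calcium, carry no rule for repeats.

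**The concern.** The neutrophil rule and the rule in 4.1 select opposite records for the same output. Two programmers following different sections would produce different by-visit neutrophil tables, and the SAP gives no means of deciding between them.

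The second issue is the shift table. The earliest-record rule is part of how the parameter is built. If it is run as written, later records are gone before any table is made, including the table meant to see every record. Changes in laboratory parameters belong to the primary safety endpoint (Protocol section 2), and the shift to worst grade is how they are to be presented (Protocol 6.4, SAP 4.9.5). A data rule that can remove the worse of two counts therefore deserves correction even if it is seldom triggered.

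**Working it through.** The plan states no figure on this point, so there is none to reproduce. The check compares the rules, applies the grading scale, and then asks how often the choice of record would matter.

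**Step 1: the rules side by side, for two results at one timepoint taken at different times.**

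| Output | General rule | Neutrophil rule | Can both hold? |
|---|---|---|---|
| By-visit summary | latest (SAP 4.1) | earliest | no |
| Worst-grade shift table | all results (SAP 4.9.5) | earliest, if applied before grading | no |
| Same clock time | not addressed separately | smallest | yes |

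**Step 2: grades.** Protocol Appendix 5 grades "Absolute neutrophil count" in the low direction only: grade 1 is 1000–1500, grade 2 is 750–999, grade 3 is 500–749 and grade 4 is below 500 per mm³. Hypothetical pairs (grade 0 = ungraded):

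| First, then repeat (per mm³) | Earliest | Latest | All data, worst |
|---|---|---|---|
| 1600, 700 | 0 | 3 | 3 |
| 900, 450 | 2 | 4 | 4 |
| 700, 1600 | 3 | 0 | 3 |
| 450, 900 | 4 | 2 | 4 |

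The worst grade over all records can never be milder than the grade of one of them. Against the all-data rule, the earliest-record rule therefore either agrees or understates. In by-visit summaries the discrepancy can go either way.

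**Step 3: how often, per repeated timepoint.** The documents give neither the spread of repeat counts nor how often repeats occur. Assumptions: two independent lognormal counts around the patient's true count *m*, with a within-patient CV of 20–30%. Then s² = ln(1 + CV²) and the log-mean is ln *m* − s²/2. Simulated pairs were graded as in step 2 under two scenarios: repeats taken regardless of the first count, and repeats taken only when the first count was at most 1500.

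| True count (per mm³) | Repeat has worse grade, any pair | Repeat has worse grade, only if first ≤ 1500 |
|---|---|---|
| 800 | 30–34% | 30–34% |
| 1200 | 24–33% | 16–22% |
| 1800 | 16–23% | 0.2–2.9% |

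For unselected pairs at a true count of 2500 the figure is about 0.7–5%, and at 3000 it is 0.03–1.3%. At 800 to 1800, the earliest and latest results give different grades in 33–69% of unselected pairs.

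**Step 4: why selection matters.** Let q be the chance that a count is at most 1500. Given a first count at or below 1500, the chance that the first is the lower of the two is 1 − q/2. For *m* = 1800 and CV 20%: s = 0.198 and the log-mean (in thousands) is 0.568, so q = Φ((0.405 − 0.568)/0.198) ≈ 0.21 and 1 − q/2 ≈ 0.90. With CV 30%, q ≈ 0.32, giving 0.84. For *m* = 1200, q is 0.89 and 0.82, giving 0.56 and 0.59. For *m* = 800, q is close to 1, giving about 0.50. The first count is thus usually the lower one when a single low reading prompted the repeat, but not in a patient whose true count is well below 1500.

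**The case against.** The strongest defence has four parts.

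- **The shift table may be safe.** The neutrophil paragraph does not mention shift tables, and the SAP does not state the order of steps. The main text of 4.9.5 sets shift tables apart and assigns them all available data. On that reading no worst grade is lost. This largely stands: loss before grading is a literal reading, not a stated step. It does not remove the ambiguity, because the rule sits in the derivation and carries no limit.
- **A specific rule may override a general one.** The earliest-record rule could be a deliberate exception to 4.1. The SAP does not say so, and an exception to 4.1 would not settle the conflict with the shift-table rule.
- **Few records are exposed.** The rule follows the summing of segments and bands, and a reported total is used without calculation. Protocol 4.5.6.1 lists neutrophils as one item of the differential and names neither component. The Schedule of Activities has its own unscheduled visit with hematology, so a later sample filed there keeps its own timepoint. Same-time duplicates keep the smaller value. All of this stands.
- **The stakes are modest.** Neutropenia is not an event of special interest (SAP 2.2.1). A clinically significant laboratory result must be reported as an adverse event regardless of this rule (Protocol 5.3.5.5). The study is descriptive: "No formal statistical hypothesis tests will be performed and all analyses are considered descriptive". This also stands.

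A reader might go further and infer that the rule deletes worse counts from the safety tables, most of all when a count is repeated because it looked abnormal. The documents do not support that. The order of steps is not given, and step 4 shows that selection on a low first count makes the first value usually the lower one, which the rule keeps. Nor does every other laboratory parameter follow the opposite rule throughout: the latest-retest rule governs by-visit summaries only, while shift tables use all results.

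**Conclusion.** Wrong as written, of minor severity. The contradiction with SAP 4.1 is plain and needs no assumption: for by-visit neutrophil summaries the two rules name different records. The conflict with the shift-table rule depends on applying the neutrophil rule literally at derivation. If it is applied that way, the error runs in one direction and understates the worst grade.

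The overall effect is probably small and cannot be computed from the documents. It is confined to repeats filed under one timepoint at different times, possibly only to summed totals, and their number is unknown. The percentages above hold per repeated timepoint under assumed CVs and true counts; they are not trial-wide rates. They are material mainly for patients whose true count is already low.

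**What to change.** In SAP 4.9.5, Total Neutrophils:

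1. Delete the earliest-record rule.
2. State that by-visit summaries of total neutrophils use the latest retest, as in SAP 4.1.
3. State that all total neutrophil results, whether derived or reported and including repeats at one timepoint, enter the worst-grade shift table.
4. Keep the smallest-result rule for records at the same time.

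The cost is a line or two of SAP text and one line of derivation code. No new data are needed.
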